8.1.2 Realization of the measurement

A linear probe will be used to measure the thickness, echogenicity and cross-sectional area of the rectus femoris, according to the procedure described in **Appendix 4**. The patient is placed in the supine position (as strict as possible), with the lower limbs in extension and in a neutral rotation position. The probe is placed on the anterior aspect of the thigh, 2/3 of the distance between the anterior superior iliac spine and the upper edge of the patella, in line with the femur.

In the transverse plane, the distance between the upper and lower fascia of the muscle body will be measured, directly on a frozen image. The thickness of the rectus femoris will be measured on the right side at rest, without patient participation. The average of 3 measurements is used to improve the reliability of the measurement.

The cross-sectional area (CSA) will also be measured. Still in the transverse plane, the cross-sectional area of the rectus femoris is measured using the "caliper" function to trace the limits of the rectus femoris and measure its area. On the same frozen image, echogenicity will be measured using the Image J software® using the entire muscle surface.

The pennation angle of the femoral rectus will also be measured in a longitudinal plane.

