5.1 Primary endpoint

The primary end point was the association between femoral rectus muscle echogenicity and the SF-36 quality-of-life score (**Appendix 1**).

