10.1 Calculation of the study size

Two groups of patients will be identified within our obesity patient population: a group of patients with low quality of life and a group with high quality of life. The median SF-36 quality of life score will be used to differentiate these 2 groups.

The echogenicity of the rectus femoris will be compared between these 2 groups, in order to evaluate the association between the muscular alteration of the rectus femoris by measuring echogenicity and the quality of life.

To our knowledge, no publication has evaluated the echogenicity of the rectus femoris in a population of obese patients. In the literature, an echogenicity of the rectus femoris of 120.9 ± 15.4 was found in a population of elderly patients (25). Given the presence of common pathophysiological mechanisms and similar sonographic characteristics (thickness and mCSA) in muscle damage between the elderly and obese patients, we hypothesize that the echogenicity of the rectus femoris in obese patients is similar to that in the elderly patient group with low quality of life.

In the absence of clinically relevant echogenicity difference data, we pragmatically expect a difference of at least 10 points (based on the alteration in muscle echogenicity of the resuscitation patient in 7 days (28)).

Thus, with a risk $\alpha = 0.05$ and a power of 90%, the number of subjects needed, for a two-sided test is 42 patients per group, or 84 in total.

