10.2 General aspects

Statistics will be primarily descriptive and will be based on means (+/- standard deviation) or medians [minimum-maximum] depending on the distribution of quantitative variables. Qualitative variables will be described in terms of numbers and percentages. Univariate comparisons will use the usual statistical tests after verification of the distribution of the variables (Chi2 or Fisher's test, t-test, anova or their non-parametric equivalents Wilcoxon and Kruskal-Wallis tests).

The risk of low quality of life in the presence of impaired muscle function will be described by Odd-Ratios.

Tests will be performed at the 5% significance level. The 95% confidence intervals will be provided for each estimate.

Calculations will be done using SPSS v21 IBM and R software (version 3.6.1, www.R-project.org).

11 Expected results in terms of scientific and professional advances

This study will evaluate the association between peripheral muscle function and quality of life impairment in obese patients hospitalized in HDJ Nutrition.

The results of this study will confirm the association of muscle status on quality of life in obese patients, which is not yet clearly established in the scientific literature. If applicable, these results will make it possible to propose non-invasive and inexpensive predictive tools to screen for muscle damage in this patient population. This screening could make it possible to propose early management programs, such as exercise re-training or the introduction of adapted physical activity.

12 Expected benefits and risks for patients

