16.4 Appendix 4: Muscle ultrasound procedure

A linear probe will be used for the measurements. A set of predefined settings of the gain and depth parameters will be used for all measurements.

Patient positioning

The patient is installed in dorsal decubitus (as strict as possible), with the lower limbs in extension and neutral position of rotation.

Placement of the probe

The probe is placed in contact with the skin via an ultrasound gel. The pressure exerted with the probe is perpendicular to the plane of the bed, in line with the femur and must be as low as possible to obtain a representative image of the muscle. Excessive pressure will cause deformation of the subcutaneous tissues and therefore of the muscle. There are two ways of orienting the probe: in the transverse or sagittal plane.

Measurements on the quadriceps

[figure not shown]

Figure 1

The probe is placed on the anterior aspect of the thigh, 2/3 of the way from the anterior superior iliac spine to the upper edge of the patella, plumb with the femur (**Figure 1**) (39). The muscle chiefs studied were the rectus femoris and the vastus intermedius.

[figure not shown]

Figure 2

Muscle thickness

In the transverse plane, measurement of the distance between the upper and lower fascias of the muscle body (Figure 2). It is measured directly on a frozen image. The thickness of the rectus femoris (DF) and the vastus intermedius (VI) will be measured on the right. The average of 3 measurements will be taken.

[figure not shown]

Figure 3

Cross-Sectional Area (CSA):

Still in the transverse plane, measure the cross-sectional area of the rectus femoris using the caliper to delineate the boundaries of the rectus femoris (Figure 3).

Pennation angle

Place the probe along the axis of the muscle. The angulation of the muscle fibers in relation to the underlying fascia becomes visible (pennation of the fibers (Figure 4). The angle between a muscle fiber and the underlying fascia will be measured only on the rectus femoris:

[figure not shown]

Figure 4

Echogenicity

Save the image used to measure the thickness and cross-sectional area. In the Image J software, delimit a 1 cm area² and analyze the variations of the gray levels. The software provides a histogram with a global value of the grey level going from 0 to 255 - 0 corresponding to black and 255 to white (28).

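### Echogenicity, the primary muscle variable, is tied to one frozen image with no stated replicate count or averaging rule, whereas thickness, a secondary variable, is averaged over three measurements

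*Combined protocol and SAP*

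**What the plan says.** Section 5.1 makes echogenicity the only muscle variable in the primary endpoint: "The primary end point was the association between femoral rectus muscle echogenicity and the SF-36 quality-of-life score". Section 10.1 turns this into a two-group comparison: "The echogenicity of the rectus femoris will be compared between these 2 groups", with the groups formed by a median split on the SF-36.

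Section 8.1.2 describes the ultrasound measurements. For thickness it gives a replicate rule and a reason: "The average of 3 measurements is used to improve the reliability of the measurement". For echogenicity it says: "On the same frozen image, echogenicity will be measured using the Image J software® using the entire muscle surface". The image meant is the one used to trace the cross-sectional area.

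Appendix 4 (section 16.4) repeats the mean of three under muscle thickness only. Its echogenicity paragraph begins "Save the image used to measure the thickness and cross-sectional area" and then has the operator analyse a 1 cm² region, whereas 8.1.2 uses the whole muscle. Neither section gives, for echogenicity, a number of images or readings, an averaging rule or a repeatability figure.

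**The concern.** The protocol states a reliability principle and applies it to a secondary measure but not to the primary one. Grey level read from a single image carries error from where and how the probe was held and from how the region was drawn. In a comparison of group means, random error of this kind does not bias the expected difference. It adds to the within-group variance, so the confidence interval is wider and the power lower than they need be. The echogenicity readings are what the sample-size calculation is about, so a loss of precision there falls directly on the primary result.

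If the number of images is simply left open, there is a second risk. Operators may take one image or several and choose among them, with no rule for which value enters the analysis.

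**Working it through.** **Inputs from the protocol**
- Difference to detect: 10 grey-level points (10.1).
- SD: 15.4, from "an echogenicity of the rectus femoris of 120.9 ± 15.4 was found" (10.1). The ± figure is read as an SD. The number of readings behind it is not stated.
- Two-sided 5% level (10.1). Section 10.2 repeats the level: "Tests will be performed at the 5% significance level".
- 42 per group (10.1). Equal groups follow from the split rule: "The median SF-36 quality of life score will be used to differentiate these 2 groups".

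**Assumed, because the documents give no figure**
- ICC of a single image within a quality-of-life group: varied from 0.70 to 0.99.
- Errors of the three images independent, given the patient.

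**Step 1: the plan's own figure.** n per group = 2 × (1.960 + 1.282)² × (15.4/10)² = 2 × 10.51 × 2.372 = 49.8, so 50 per group (51 with the exact t-test). The stated 42 at two-sided 90% power is not reproduced; it matches a one-sided 5% t-test. At 42 per group the noncentrality is 10 / (15.4 × √(2/42)) = 10 / 3.361 = 2.98 on 82 degrees of freedom. Two-sided power is then 83.7% (84.5% by the normal approximation). This 83.7% is the reference for what follows.

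**Step 2: effect of averaging.** With single-reading SD s₁, the SD of the mean of three is s₃ = s₁ × √(ICC + (1 − ICC)/3).

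Example at ICC 0.80: the factor is √(0.80 + 0.0667) = 0.931.
- Case A, 15.4 is a single-reading SD: s₃ = 15.4 × 0.931 = 14.34, noncentrality 3.20, power 88.5%.
- Case B, 15.4 is already the SD of a mean of three: s₁ = 15.4 / 0.931 = 16.54, power with one reading 78.2%.

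**Step 3: the range** (two-sample t-test, two-sided 5%, difference 10, 42 per group)

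| ICC | A: SD, mean of 3 | A: power, mean of 3 (one reading 83.7%) | B: SD, one reading | B: power, one reading (mean of 3 83.7%) |
|---|---|---|---|---|
| 0.99 | 15.35 | 83.9% | 15.45 | 83.4% |
| 0.95 | 15.14 | 84.9% | 15.66 | 82.4% |
| 0.90 | 14.88 | 86.1% | 15.94 | 81.1% |
| 0.80 | 14.34 | 88.5% | 16.54 | 78.2% |
| 0.70 | 13.77 | 90.8% | 17.22 | 74.9% |

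The advantage of three images over one is therefore 0.2 to 7.1 power points in case A (83.9 − 83.7; 90.8 − 83.7) and 0.3 to 8.8 in case B (83.7 − 83.4; 83.7 − 74.9).

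**The case against.** The strongest objection is that the protocol never says echogenicity is read once. That is right. A single reading is an inference from the singular image in 8.1.2 and Appendix 4. Thickness is also measured on a frozen image and is still averaged over three, and the text does not say whether those three are separate images or three caliper placements on one. What stands is narrower: for the primary variable the text points to one image and gives no replicate count or averaging rule. The same change cures both possibilities.

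Second, the noise may be small. The protocol fixes gain and depth, asks for minimal probe pressure, fixes the probe site and requires more than 100 supervised scans of each operator. No repeatability figure is given, and at an ICC of 0.95 or above the gain in case A is at most 1.2 points. If 15.4 is a single-reading SD, the planning figure already contains this error and averaging is a bonus, not a repair. Error shared by all images in one operator's session would not average out, so the gains in the table are upper limits at each ICC. All of this stands, and it is why the size can only be given as a range.

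Third, two supporting arguments that a reader might reach for do not hold. Grip and quadriceps strength use three efforts, but sections 7.2.1 and 7.2.2 keep the maximum, so they are no precedent for averaging. Appendix 4 warns that pressure deforms the tissue; it does not say that grey level changes with pressure.

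**Conclusion.** The point holds as a cheap improvement to the measurement of the primary variable. Under either reading of the 15.4, three independent images do better than one. The benefit runs from negligible at ICC 0.99 to about 7 power points (case A) or 9 (case B) at ICC 0.70. This rests on a true difference of 10, equal groups of 42, no dropout and independent image errors.

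A reader might infer that the single image explains why power is about 84% and not 90%. The documents do not support that. The shortfall arises in the calculation in 10.1 with the SD taken as given, and needs its own correction. In case A averaging reaches 90% only at the low end of the assumed reliability range, ICC 0.70; at ICC 0.80 it gives 88.5%. Nor do the documents show that single-image error is large; they are silent on it.

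**What to change.** In both 8.1.2 and Appendix 4:

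1. Reconcile the region analysed, whole muscle or 1 cm² area, to one rule. Without this, averaging would not give a defined primary variable.
2. Acquire and save three transverse images per patient, repositioning the probe each time. Re-reading one image would reduce only tracing error and leave acquisition error untouched.
3. Read echogenicity on each image with that one rule and analyse the mean of the three.
4. Keep the three values and report the ICC. Section 10.1 knows of no published rectus femoris echogenicity in obese patients, so this figure would be useful in itself.

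The cost is two more acquisitions and readings per patient, by the same operator in the same session: 84 × 2 = 168 over the study, or fewer if the three thickness measurements already come from three separate images. No extra visits or patients are needed. The sample size in 10.1 should be corrected separately.

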8.2 Quality of Life Scale

The SF-36 Quality of Life Questionnaire assesses health status independent of causative pathology, gender, age, and treatment. This scale can be administered as a self- or hetero-questionnaire, and requires only 5 to 10 minutes. Its 36 items assess 8 dimensions (**Appendix 1**):

- Limitations due to physical condition;
- Physical pain;
- Perceived health;
- Vitality;
- Life and relationship with others;
- Limitations due to physical condition;
- Mental health.

A sub-score for each component can be calculated, ranging from 0 to 100. The calculation is done according to an established algorithm.

9 Conduct of the research

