8.1 Muscle ultrasound

8.1.1 Operator training

Ultrasound measurements are performed by one of the investigating physical therapists. The physiotherapist is authorized to perform ultrasound subject to training (Avis du Conseil National de l'Ordre des Masseurs-Kinésithérapeutes (2015)). The training of the operator corresponds to the following:

- 3 days of theoretical and practical training;
- Over 100 ultrasounds supervised by an experienced practitioner;

Similarly, all the physiotherapists performing the ultrasound scans are already involved in other research projects using lung, diaphragm and peripheral muscle ultrasound:

<https://clinicaltrials.gov/ct2/show/NCT02474797>,

<https://clinicaltrials.gov/ct2/show/NCT02881814>,

<https://clinicaltrials.gov/ct2/show/NCT04373811>

and

<https://clinicaltrials.gov/ct2/show/NCT04800783>.

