9.3 Visit of the physiotherapist

The physical therapist visit takes place after the inclusion visit. The following measurements will be performed:

- Peripheral muscle ultrasound measurements:
 - Femoral rectus thickness;
 - Cross-sectional area of the femoral rectus;
 - Echogenicity;
 - Pennation angle.
- Grip force;
- Quadriceps FMV;
- Quality of Life Questionnaire (SF-36).

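### The plan leaves open who administers the SF-36, in which mode and when, and does not mask the echogenicity reader, so the two sides of the primary association are not kept independent

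*Combined protocol and SAP*

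**What the plan says.** **SF-36 mode.** Section 8.2: "This scale can be administered as a self- or hetero-questionnaire, and requires only 5 to 10 minutes". No section chooses between the two modes, names an administrator or asks for the mode to be recorded.

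**SF-36 timing.** Section 9.3: "The physical therapist visit takes place after the inclusion visit. The following measurements will be performed". The list that follows runs ultrasound, grip force, quadriceps force, and last "Quality of Life Questionnaire (SF-36)". The summary table in 9.5 puts all of these in one visit column and gives no order within it.

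**Ultrasound operator.** Section 8.1.1: "Ultrasound measurements are performed by one of the investigating physical therapists".

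**Echogenicity reading.** Section 8.1.2: "On the same frozen image, echogenicity will be measured using the Image J software® using the entire muscle surface". Appendix 4 first says "Save the image used to measure the thickness and cross-sectional area", and then "In the Image J software, delimit a 1 cm area² and analyze the variations of the gray levels". Neither place names the reader or says what the reader may know about the patient.

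**Use of the two measurements.** Section 5.1 makes their association the primary endpoint. Section 10.1 tests it by comparing echogenicity between patients below and above the median SF-36 score.

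**The concern.** An association study needs its two measurements to be made independently of each other. Here there are two open routes by which one could leak into the other.

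- **From muscle to questionnaire.** If the SF-36 is given as an interview after the scan and strength tests, the interviewer may be a study physiotherapist who has seen the muscle and the strength values. The study hypothesis (section 3) is directional: poorer muscle function goes with poorer quality of life. Wording, prompting or the patient's own impression of the tests could then move the answers in the expected direction.
- **From questionnaire to muscle.** Echogenicity depends on a region that someone delimits. A reader who knows the SF-36 answers or the strength values could, without intending to, choose the region differently.

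Both routes favour finding an association. The planned tests are univariate (section 10.2). If mode and order are not recorded, the influence on the SF-36 side cannot be examined afterwards, even as a sensitivity analysis.

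**Working it through.** **1. The plan's own figure.** Inputs from section 10.1: difference 10, SD 15.4, two-sided alpha 0.05, power 90%, 42 per group.

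n per group = 2 × (1.960 + 1.282)² × (15.4/10)² = 49.8, so 50 per group and 100 in total (51 per group with the t-test).

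The stated 42 is not reproduced. It gives two-sided power of 84.5% (normal) or 83.7% (t-test), and it is close to a one-sided 90% calculation (41 normal, 42 t-test). This is a separate matter. It is noted here only because 42 per group and SD 15.4 are used below as stated.

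**2. Which safeguards are stated.**

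| Question | What the documents state |
|---|---|
| SF-36 mode | Both modes possible, none chosen (8.2) |
| SF-36 administrator | Not named |
| Order within the visit | Listed last, no sequence stated (9.3, 9.5) |
| Recording of mode | Not required |
| Masking of the Image J reader | Not stated (8.1.2, Appendix 4) |
| Region read | Entire muscle (8.1.2) or 1 cm² (Appendix 4) |

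**3. What a spurious difference would do.** The documents give no bias size, so 2, 3 and 5 grey levels are assumptions. They are 20%, 30% and 50% of the planned difference of 10. The true association is set to zero.

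Standard error = 15.4 × √(2/42) = 3.36. Noncentrality = bias / 3.36, with 82 degrees of freedom.

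| Assumed bias | Noncentrality | Two-sided rejection rate |
|---|---|---|
| 0 | 0 | 5.0% |
| 2 | 0.60 | 9.0% |
| 3 | 0.89 | 14.3% |
| 5 | 1.49 | 31.3% |

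**4. The same question without choosing a side.** Step 3 shifts echogenicity only. A simulation (10,000 runs, 84 patients, median split, t-test) instead assumes a spurious correlation r between the two measurements, whichever route produced it.

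| Assumed r | Mean group difference (points) | False-positive rate |
|---|---|---|
| 0 | 0.0 | 5% |
| 0.05 | 1.2 | 6% |
| 0.10 | 2.4 | 11% |
| 0.15 | 3.7 | 20% |
| 0.20 | 4.9 | 31% |

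The two calculations agree: a spurious difference of about 5 points gives about 31% in each. A small induced correlation would matter. Neither calculation shows that one is present.

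**The case against.** The case against is substantial, and much of it limits the point.

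- **Self-completion is the natural reading of the form.** Section 8.2 describes what the instrument allows and does not order an interview. The Appendix 1 form asks the respondent to tick and circle answers. This stands: with self-completion the influence on the SF-36 side is much smaller. But the form does not fix the mode, and 8.2 leaves the other one open.
- **A reader might infer that one person makes both measurements.** The documents do not say so. Section 8.1.1 refers to one of several physiotherapists, and nobody is named for the SF-36. A single physiotherapist visit makes this possible, not certain.
- **A reader might infer that patients answer straight after maximal effort.** That rests on list order alone. Such an effect would also act first on the strength associations, which are secondary.
- **The echogenicity side has some protection.** Appendix 4 fixes gain and depth settings in advance, and the value is a software grey level. Reading the entire muscle leaves little choice of region. If the cut is the sample median, final group membership is unknown until recruitment ends. This reduces the risk. It does not remove it, because a reader can still know the raw answers, and the 1 cm² area in Appendix 4 leaves more choice.
- **The routes do not all operate together.** If the SF-36 comes last, it cannot affect image acquisition. If Image J is read later, the echogenicity value is unknown during the questionnaire, although the image has been seen. Mixed modes unrelated to echogenicity would mainly add noise and weaken the association.
- **A reader might conclude that no later step could repair the bias.** That is too strong. Images are saved, so a masked re-reading could deal with reader bias. Only influence on the SF-36 answers cannot be undone.

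**Conclusion.** The point holds as a gap in procedure. The plan does not fix SF-36 mode, administrator or order, and does not mask the echogenicity reader, so it permits each side of the primary association to be influenced by knowledge of the other. It does not show that this will happen.

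The size is unknown. The range of about 9% to 31% rests on an assumed spurious difference of 2 to 5 grey levels, SD 15.4, 42 per group and no true association. It must not be read as an estimate of this study's false-positive rate. If patients in fact complete the form alone before any test, the questionnaire route largely closes. The scanning physiotherapist could then know the answers, so the reading rule is needed in either order.

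The change should be made because it costs little, and because bias in the SF-36 answers cannot be corrected once they are collected.

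**What to change.** **Sections 8.2 and 9.3.** State that the patient self-completes the SF-36 before the ultrasound and strength tests, for example after consent at reception. Sections 7.1 and 9.1.2 already place the nurse's reception, and the information given to the patient, at the start of the day. Where help is needed, it comes where possible from existing staff other than the scanning physiotherapist. Record the mode (self or assisted) for each patient.

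**Section 8.1.2 and Appendix 4.** State that the existing team reads the saved images in Image J later, in batches. Images carry a study number only, and SF-36 and strength data are not to hand. The identification code in 14.8 contains initials, so the image label should omit them. While these passages are open, reconcile the region: entire muscle in one, 1 cm² in the other.

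**Cost.** A changed order on the day, a labelling rule for images that are already saved, one added data item and a later reading session. No extra reader, no added patient procedure and no change to the sample size.
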